## **3 Study Objectives**

### **3.1 Primary Objective:**

Evaluate the long-term effectiveness of prostatic artery embolization (PAE) with Embosphere Microspheres as assessed by the International Prostate Symptom Score (IPSS) for those subjects who are eligible to complete a baseline IPSS for comparative purposes.

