## **6.2 Prostatic Artery Embolization (PAE) Procedure Information**

The following procedural data will be collected:

- Date of procedure
- Date and time of discharge
- Embolization start and end time
- Access site (Femoral/Radial)
- Was the PErFecTED technique used? (If yes, prostate lobe(s) used on)
- Was Foley catheter with contrast used?
- Lobes embolized (Right/Left/Both)
- Size of Embosphere Microspheres
- Total Volume Administered
- Device or Procedure-related adverse events

Patients will be given a form on which to record Device or Procedure-related adverse events during the first month post procedure.

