## **6.3 Visit 1: 4 Weeks ( $\pm 1$ week) Follow-Up**

The following information will be collected:

- Device or Procedure-related adverse events
- Changes in indwelling urinary catheter use
- BPH related medications
- Additional prostate procedures and/or imaging
- Prostate specific antigen (PSA), if done

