## 8.4 Analysis Populations

### 8.4.1 Full Analysis Set (FAS)

Includes all patients that were enrolled except those that withdrew consent before the index procedure. The FAS is the population that will be used in determining endpoints except for efficacy endpoints

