### 8.4.2 Evaluable Analysis Set (EAS)

Includes FAS patients where there are no significant deviations (e.g. not meeting the inclusion/exclusion criteria) from the protocol that did not have an indwelling catheter at the end of the procedure.

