## 8.5.2 Analysis of the Primary Endpoint

The stratified sample mean change from baseline in 12 month IPSS is estimated as follows.

$$\bar{x} = \sum_{h=1}^L \frac{N_h}{N} \sum_{i=1}^{n_h} \frac{X_{hi}}{n_h} = \sum_{h=1}^L \frac{N_h}{N} \bar{x}_h$$

where  $\bar{x}$  is the stratified sample mean,  $L$  is the number of strata,  $X_{hi}$  is change from baseline in 12 month IPSS for the  $i^{th}$  patient in the  $h^{th}$  stratum,  $N$  is the overall sample size and  $N_h$  is the sample size in stratum  $h$

It can be shown in T. Yahane(1967) that the expected value and variance of  $\bar{x}$  ( $V(\bar{x})$ ) assuming sampling without replacement are

$$E(\bar{x}) = \mu$$

$$V(\bar{x}) = \sum_{h=1}^L \left(\frac{N_h}{N}\right)^2 \left(\frac{N_h - n_h}{N_h n_h}\right) S_h^2$$

$$S_h^2 = \frac{1}{N_h - 1} \sum_{i=1}^{N_h} (X_{hi} - \mu_h)^2$$

where

The 95% confidence interval ( $CI(\mu)$ )s calculated as follows:

$$CI(\mu) = \bar{x} \pm z_{1-\alpha/2} \sqrt{\hat{V}(\bar{x})}$$

where  $\alpha$  is the type I error and  $\hat{V}(\bar{x})$  is the unbiased estimator of  $V(\bar{x})$  and is calculated as follows:

$$\hat{V}(\bar{x}) = \sum_{h=1}^L \left(\frac{N_h}{N}\right)^2 \left(\frac{N_h - n_h}{N_h n_h}\right) S_h^2$$

$$s_h^2 = \frac{1}{n_h - 1} \sum_{i=1}^{n_h} (X_{hi} - \bar{x}_h)^2$$

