## 8.5.3 Analysis of the Secondary Endpoints

### 8.5.3.1 IPSS changes over time

The changes over time in the IPSS using the EAS will be modeled using a linear mixed model where country and patient will be considered a random effect. If there is evidence of non-linearity, a nonlinear mixed-effects model using a 3rd-degree

 Tibshirani, Robert (1996). "Regression Shrinkage and Selection via the lasso". Journal of the Royal Statistical Society. Series B (methodological). Wiley. 58 (1): 267–88. JSTOR 2346178.

polynomial will be implemented. The predicted curve and 95% confidence interval will be reported. Missing data will not be imputed.

Sensitivity analyses using complete cases and missing values replaced with an age-specific average will be performed.

A multivariate linear model will be developed to predict the IPSS changes over time. Univariate analysis will be performed analyses for all the baseline characteristics. Based on those results combined with clinical judgment, a final set of baseline characteristics will be created for use in the multivariate model. The LASSO regression analysis method will be used to perform variable selection and regularization.

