## 18 Safety Medical Monitor

An independent safety medical monitor shall be responsible for systemic review and adjudication of specified events (e.g., all treatment-related adverse events and all deaths) . At a minimum, assess the reported event with the associated documented risks of device, vascular embolization, and PAE treatment.

Potential risk for Embosphere Microspheres:

- Immune reaction in patients who are hypersensitive to collagen or gelatin (careful consideration should be given prior to using this product in patients who are suspected to be allergic to injections containing gelatin stabilizers)

Potential risk for vascular embolization:

- Paralysis resulting from untargeted embolization or ischemic injury from adjacent tissue edema
- Undesirable reflux or passage of Embosphere Microspheres into normal arteries adjacent to the targeted lesion or through the lesion into other arteries or arterial beds, such as the internal carotid artery, pulmonary, or coronary circulations
- Pulmonary embolism
- Ischemia at an undesirable location, including ischemic stroke, ischemic infarction (including myocardial infarction), and tissue necrosis
- Capillary bed occlusion and tissue damage
- Vessel or lesion rupture and hemorrhage
- Vasospasm
- Recanalization
- Foreign body reactions necessitating medical intervention
- Infection
- Complications related to catheterization (e.g., hematoma at the site of entry, clot formation at the tip of the catheter and subsequent dislodgment, and nerve and/or circulatory injuries, which may result in leg injury)
- Allergic reaction to medications (e.g., analgesics)
- Allergic reaction o contrast media or embolic material
- Pain and/or rash, possibly delayed form the time of embolization
- Death
- Blindness, hearing loss, loss of smell, and/or paralysis

PAE specific potential complications:

- Non-targeted embolization of the rectum, bladder, scrotum, penis, or other areas
- The most frequent post-procedure complication includes “Post-PAE Syndrome,” which includes nausea, vomiting, fever, pelvic pain, burning sensation, dysuria, and frequent or urgent urination
- Skin burn (radiation exposure) from prolonged fluoroscopy time
- Blood in urine, semen, or stool
- Bladder spasm
- Hematoma at the catheter site
- Urinary tract infection
- Urinary retention
- Constipation

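### The efficacy analysis set is fixed by catheter status at the end of the procedure, while the primary objective defines its population by eligibility for a baseline IPSS

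*Combined protocol and SAP*

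**What the plan says.** The combined protocol and SAP describes the efficacy population in several places.

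- **Section 3.1 (primary objective):** effectiveness by IPSS "for those subjects who are eligible to complete a baseline IPSS for comparative purposes". Section 4 asks every subject for an IPSS but does not require it of men with an indwelling catheter.
- **Section 8.4.1:** "The FAS is the population that will be used in determining endpoints except for efficacy endpoints". Only one other set is defined, the EAS.
- **Section 8.4.2:** the EAS is FAS patients without significant deviations "that did not have an indwelling catheter at the end of the procedure". It does not mention a baseline IPSS.
- **Section 8.5.2 (primary analysis):** "The stratified sample mean change from baseline in 12 month IPSS is estimated as follows". No analysis set is named.
- **Section 8.5.3.1:** "The changes over time in the IPSS using the EAS will be modeled using a linear mixed model". Section 8.5.3.6 also uses the EAS, for SHIM.
- **Section 8.5.1.7:** assigns the secondary endpoints to the FAS. Section 8.1.2 lists IPSS at 3, 12 and 24 months among them.
- **Section 8.5.2.1:** fills a missing IPSS with an age-specific average and makes no exception for men exempt from the questionnaire.

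On catheter data, section 6.1 lists baseline use among evaluations collected if done. The only catheter item among the procedure data in section 6.2 is "Was Foley catheter with contrast used". Section 6.3 collects "Changes in indwelling urinary catheter use" at 4 weeks.

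**The concern.** The study has a single arm and its main result is one mean change, so the analysis set decides what that number means. The objective selects men by a baseline property. The EAS selects them by a status that exists only once the procedure is over.

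That status may partly reflect treatment or local practice. Section 18 lists "Urinary retention" as a PAE-specific complication, without giving its timing. Section 6.2 shows that a Foley may be used during the procedure, and nothing says whether one still in place at the end counts as indwelling.

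Two things are at stake: whether the primary estimate answers the stated objective, and whether two analysts working from the same data would build the same set.

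**Working it through.** **1. The two rules side by side.** Section 3.1 does not define eligibility. I read it through section 4, where an indwelling catheter is what removes the requirement.

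| Patient | Objective (3.1) | EAS (8.4.2) |
|---|---|---|
| Baseline IPSS, no catheter at end of procedure | in | in |
| Baseline IPSS, catheter at end of procedure | in | **out** |
| Catheter at baseline, no IPSS, still in place at end | out | out |
| Catheter at baseline, no IPSS, out by end | out | **in** |

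Rows two and four disagree. In row four the change score has no observed baseline, and section 8.5.2.1 would supply one. Row four may be rare, since sections 3.2, 8.1.2 and 8.5.3.7 treat removal as a follow-up event. The documents give no frequency for either row.

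**2. Which set is used.** Section 8.4.1 takes efficacy endpoints out of the FAS, which leaves the EAS for the primary analysis. For IPSS over time, section 8.5.1.7 points to the FAS and section 8.5.3.1 to the EAS. The sensitivity analyses in sections 8.5.2.1 and 8.5.3.1 deal with missing values, not with men removed by the set definition.

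**3. Data source.** Table 1 marks catheter use at baseline, Visits 2 to 4 and unscheduled visits, but not at the PAE procedure or Visit 1. Section 6.3 does collect changes at 4 weeks ± 1 week, so that visit falls 21 to 35 days after the procedure. Those changes can reach back to the procedure. Derivation may therefore be possible, but no rule is written.

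**4. Size of a shift.** Let p be the share of men in the objective's population whom the EAS drops (row two), d their shortfall in mean improvement, and m the mean improvement of the rest. The objective's mean is (1 − p)m + p(m − d) = m − pd. The EAS mean is m. The difference is p × d.

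| p | d for a 0.5-point shift (0.5/p) | d for a 1-point shift (1/p) |
|---|---|---|
| 5% | 10 | 20 |
| 10% | 5 | 10 |
| 20% | 2.5 | 5 |

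These are thresholds, not estimates. For scale, mean IPSS in the 286-patient cohort of section 1 fell by 21.5 − 6.2 = 15.3 points.

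**5. Precision.** Inputs from section 8.3: SD 8.5, two-sided 95% interval of width 2 (half-width 1), 10% missing, up to 500 patients.

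- Plan's figure: (1.96 × 8.5 / 1)² = 277.6, so 278; 278 / 0.9 = 308.9, so 309. This does not reproduce 500. That figure is a ceiling, and the stratum weights used in the software are not given, so it is a separate matter.
- Assumed share catheterised at baseline without an IPSS: 54/286 = 18.9% (section 1 cohort).
- Evaluable: 500 × (1 − 0.189) × 0.9 ≈ 365, before exclusions for deviations.
- Simple half-width, without the finite-population factor in section 8.5.2: 1.96 × 8.5 / √365 = 0.87. There are 365 − 278 = 87 men to spare, and the target holds until 1 − 278/450 = 38% are catheterised.
- Unequal countries: four shares within 15% to 25% sum to 100% only if all are 25%. Take 15/20/20/25%, rescaled to 18.75/25/25/31.25%, with equal country weights. Then D = Σ 0.25²/f = 1.033, the need is 277.6 × 1.033 = 286.8, so 287, and the half-width is 0.872 × √1.033 = 0.89. There are 78 men to spare, and the target holds to about 36%.

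**The case against.** The strongest reply is that the effect on the result is not shown. That stands. No section gives p or d, and some thresholds are extreme. At p = 5%, a 1-point shift needs d = 20, so against a 15.3-point mean improvement the excluded men would have to worsen by about 5 points. A reader might infer that the EAS flatters the device by removing poor responders. The documents do not support that, because d could be zero or negative.

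A second reply is that section 8.5.1.7 puts secondary endpoints in the FAS, which would bring the excluded men back into a 12-month IPSS analysis. This stands in part. It rules out a flat statement that no planned analysis includes them. But sections 8.4.1 and 8.5.3.1 say otherwise, so the reply shows a further conflict, not a safeguard.

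Third, the status may be recoverable from baseline use, changes reported at 4 weeks, unscheduled records or adverse events recorded at the procedure, and the eCRF is not in the documents. It would be too strong to say the status was not collected. What stands is that no listed procedure item records it and no derivation is given.

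Fourth, the documents mostly use the word indwelling for men managed with a catheter and name the procedural Foley separately, so the intended meaning may be clear to the authors. A short definition would settle it.

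None of these replies reconciles section 3.1 with section 8.4.2.

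**Conclusion.** The point holds as a conflict between rules. Sections 3.1 and 8.4.2 select different men, the second by a criterion fixed after treatment began, and the text does not settle which set serves the primary analysis or IPSS over time. It should be fixed before analysis.

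The size and direction of any bias are unknown. The shift is p × d, and it is zero if the excluded men are few or improve as much as the others.

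A reader might also infer that restricting the set by baseline eligibility would endanger the ±1 target. It would not under the stated assumptions (18.9% catheterised at baseline without an IPSS, 10% missing, 500 enrolled, country shares summing to 100% and within or close to the stated range). About 365 men remain, with a half-width of 0.87 to 0.89. The question is who is analysed.

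Confidence is high on the population mismatch and moderate on the data-source gap, because the eCRF is not shown.

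**What to change.** 1. **Define the primary effectiveness set by baseline status.** Take FAS patients with no indwelling catheter at baseline, or with a baseline IPSS completed despite one, whatever their catheter status after the procedure. Keep the condition on significant deviations. Do not require a completed baseline IPSS of every man, which is narrower than section 3.1. Eligible men with a missing baseline go under the missing-data rule; men exempt from the baseline IPSS do not have one imputed.
2. **Name this set in section 8.5.2**, and bring sections 8.4.1, 8.5.1.7 and 8.5.3.1 into line with it.
3. **Use one catheter definition for analysis**, which does not count a catheter placed only for the procedure. Anchor the removal denominator in section 8.5.3.7, now tied to a catheter during the procedure, to baseline use. Record that use for every patient and not only if done (section 6.1). Add the 24-month removal report that section 8.1.2 lists and section 8.5.3.7 omits.
4. **Keep the current EAS as a sensitivity analysis** only if end-of-procedure status was recorded or can be derived by a written rule.

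The cost is minor: SAP wording and a completeness check of baseline catheter use.

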## 8.5 Statistical Analyses

### 8.5.1 General Approach

Except where otherwise specified, the following general principles apply to the planned statistical analyses. All statistical analyses will be conducted using {SAS version 9.4 or later (SAS Institute Inc., Cary, NC)} or other widely accepted statistical or graphical software as required.

#### 8.5.1.1 Descriptive Statistics

Continuous data will be summarized with mean, standard deviation, median, minimum, maximum, and number of evaluable observations. Categorical variables will be summarized with frequency counts and percentages. Confidence intervals may

be presented, where appropriate, using the t-distribution for continuous data and exact binomial method for categorical variables.

### **8.5.1.2 Timing**

*Overall Timing:* Day 0 is the date of the procedure. Study Day will be calculated relative to the randomization as follows:

- Study Day = Assessment Date – Procedure Date

*Duration:* Duration variables will be calculated as follows:

- Duration Days = Start Date – End Date

A day is defined as 24 hours, from 0:00 to 23:59. 24:00 means 0:00 of the next day.

Each subject duration in the study will be based on the last study contact date, which is the latest date of all follow-up visits, assessments, adverse event onset or resolution, and study exit, including date of death.

*Visit Windows:* Unless otherwise specified, visit assessments will be analyzed for each analysis time point according to the study visit entered in the electronic Case Report Form (eCRF) to determine if the visit was within compliance.

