### 8.5.1.6 Adverse Event Dates

More generally, in the case of partial adverse event onset date or date of death, the unknown portion of the date of the event will be imputed. If the month and year are known, the 15th of the month will be used for analysis. If only the year is known, the event will be analyzed as if it occurred on June 30th of the known year. In the rare case that the date is fully unknown, the date will be imputed as the initial treatment date. Imputation of partial dates is subject to the condition that it must occur on or after the initial treatment date. In the case where the imputed date is before the initial treatment date, the date of the initial treatment will be used. As death cannot occur before any documented subject contact, for date of death, the imputed date of death must occur on or after the last known contact in the study.

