### 8.5.4 Safety Analyses

All device or procedure related adverse events (AEs) collected will be summarized cumulatively throughout the follow-up time. The frequency count of AEs and the unique number of subjects who had the AEs will be presented. Also, the frequency and percentage of patients who had a Serious AE (SAE), or a treatment-related serious AE will be tabulated separately. If a patient experienced multiple AEs, only the most severe event or the most intense relationship to the study device would be counted within an AE code. The following information will be reported about each AE; start date, stop date, severity, relationship, expectedness, outcome, and duration.

The time-sensitive nature of any response variable may be displayed by using a Kaplan-Meier plot.

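### Section 8.5.1.2 reverses the operands of the duration formula, so adverse event durations computed by it have the right size but the wrong sign

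*Combined protocol and SAP*

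**What the plan says.** Section 8.5.1.2 (Timing) gives two date rules, one directly after the other.

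- Study day: "Study Day = Assessment Date – Procedure Date", with Day 0 set at the procedure. The sentence that introduces it reads "Study Day will be calculated relative to the randomization as follows".
- Durations: "Duration variables will be calculated as follows", followed by "Duration Days = Start Date – End Date".

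Three other places determine how far the second rule reaches.

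- Section 8.5.1 puts it in force by default: "Except where otherwise specified, the following general principles apply to the planned statistical analyses". No other section states a different duration formula.
- Section 8.5.4 lists what is reported for each adverse event: "start date, stop date, severity, relationship, expectedness, outcome, and duration".
- Section 8.5.1.6 fills in partial onset dates: "If the month and year are known, the 15th of the month will be used for analysis". When only the year is known, June 30th is used. The one bound on an imputed onset is a lower one: "Imputation of partial dates is subject to the condition that it must occur on or after the initial treatment date".

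**The concern.** A duration should be the later date minus the earlier one. The rule as printed does the opposite, and it is a working instruction, not background text. A program written exactly to the plan would list negative adverse event durations. A program that silently swaps the terms would give sensible values but no longer match the plan, and anyone checking output against the plan would have to query the difference.

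What is at stake is one reported safety variable, together with any other duration computed by the same rule. Time in the study, which section 8.5.1.2 bases on the last contact date, is a likely candidate.

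**Working it through.** The plan gives no numerical duration to reproduce, so the check is date arithmetic on the rule itself.

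**Step 1: does the dash mean subtraction?** The Study Day rule just above it uses the same sign. With a procedure on 1 March 2021 and a visit on 1 March 2022, assessment date minus procedure date is 365, which is the sensible answer with Day 0 at the procedure. So the dash is a minus sign, and in that rule the later date comes first.

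**Step 2: apply the duration rule as printed and with the terms swapped.** Dates are illustrative.

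| Start | End | As printed (start − end) | Swapped (end − start) | Swapped, plus 1 day |
|---|---|---|---|---|
| 1 Mar 2021 | 1 Mar 2021 | 0 | 0 | 1 |
| 1 Mar 2021 | 2 Mar 2021 | -1 | 1 | 2 |
| 1 Mar 2021 | 11 Mar 2021 | -10 | 10 | 11 |
| 1 Mar 2021 | 1 Mar 2023 | -730 | 730 | 731 |

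In study days, an event from day 3 to day 10 gives 3 − 10 = -7 as printed and 10 − 3 = 7 when swapped. The absolute values agree in every row; only the sign differs. The last column shows a choice that the plan leaves open: without the extra day, an event that starts and stops on the same date has a duration of 0.

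**Step 3: does the rule reach a reported variable?** Section 8.5.4 reports a duration for each adverse event beside its start and stop dates. Section 8.5.1 makes the section 8.5.1.2 rule the default, and nothing overrides it. So it does.

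**Step 4: test the edge case from date imputation.** Suppose the onset is known only as March 2021, the stop date is known to be 10 March 2021, and the initial treatment was earlier. Section 8.5.1.6 sets the onset to 15 March.

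- As printed: 15 − 10 = +5 days.
- Swapped: 10 − 15 = -5 days.

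Swapping the terms is therefore not enough to guarantee a non-negative duration; the imputed onset also needs an upper bound at the stop date. That bound cannot clash with the existing lower bound. Section 9 counts only events that begin on or after the PAE date, so a valid stop date is never before treatment.

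**Step 5: look for an endpoint that uses a duration.** The primary endpoint is the 12-month IPSS (section 8.1.1). The secondary endpoints in section 8.1.2 are IPSS over time, adverse event rates, technical success, catheter removal, further treatments and SHIM change. Event rates are subjects with an event divided by evaluable subjects (section 8.5.1.5). None is an event duration.

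**The case against.** The strongest reply is that this is an obvious slip with little practical risk. The line above it shows the intended direction, a negative duration would be noticed on first output, and the listing carries both dates, so a reader could restore the sign. All of that stands, and it limits how much weight the point can bear. It does not make the printed rule correct, and the plan offers no other rule to fall back on.

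A reader might also infer three stronger things, which the documents do not support.

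- *That every adverse event duration would be zero or negative.* Step 4 shows an exception: an imputed onset that falls after a known stop date gives a positive value under the printed rule. This is an artefact of imputation and does not rescue the formula, but it rules out the word every.
- *That mean and median durations would be reported with the wrong sign.* Section 8.5.4 plans duration as an item for each event. Section 8.5.1.1 says how continuous data are summarized in general, but no section names a summary of adverse event duration.
- *That study days are miscalculated because they refer to a randomization.* The study is single arm (section 4), so the word is out of place. But the section puts Day 0 at the procedure and the formula subtracts the procedure date, so the values are right as written.

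**Conclusion.** The concern holds as a minor error in a stated rule. Followed literally, section 8.5.1.2 gives a sign-reversed duration for any event whose stop date is after its start date: -7 instead of 7 for an event from day 3 to day 10. Magnitudes are unaffected, and no primary or secondary endpoint changes.

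This rests on two readings: that the dash is a minus sign, which the neighbouring Study Day rule supports, and that the section 8.5.1.2 rule governs the durations in section 8.5.4, which follows from the default clause in section 8.5.1 and the absence of any other formula. Whether the analysis programs would in fact follow the printed order cannot be told from the documents.

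**What to change.** 1. In section 8.5.1.2, change the rule to `Duration Days = End Date – Start Date`.
2. In the same place, state whether 1 day is added, so that it is clear whether a same-day event lasts 0 days or 1 day.
3. In section 8.5.1.6, add that an imputed onset date may not be later than a known stop date. In the example in step 4, a cap at 10 March gives 10 − 10 = 0 days (or 1 with the added day) in place of -5.
4. As an editorial correction only, have the sentence that introduces Study Day refer to the index procedure date in place of randomization. The formula beneath it needs no change. Naming the index procedure also helps because sections 6.6 and 7 allow repeat PAE and count follow-up from the first one.

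The cost is a few words in two subsections. No data collection, sample size or endpoint definition changes.

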## 6.6 Additional Evaluations

Data will also be collected for additional evaluations that occur at any times outside of the above protocol-defined timepoints. If a patient receives any additional PAE procedures with Embosphere Microspheres, he will remain in the study, and the schedule for the follow-up evaluations will begin according to the date of the first PAE with Embosphere Microspheres procedure until the subject reaches a total of 24 months follow-up. End of study at 24 months is calculated on subject's first PAE procedure and not any additional PAE procedures.

Table 1. Schedule of Events

Table 1 identifies the Schedule of Events below. Follow-up may occur in the form of an in-person office visit, phone call, or mail. Information may be collected by email or text if the patient has documented that this is acceptable.

	Baseline	PAE Procedure	Visit 1	Visit 2	Visit 3	Visit 4	Unscheduled Visits
			4 Weeks (±1 week/± 7 days)	3 Months (±2 weeks/± 14 days)	12 Months (±8 weeks/±56 days)	24 Months (±8 weeks/±56 days)	
Informed Consent	X						
Demographics	X						
Prostate Size Assessment	X 						
Prior BPH Procedures	X						
Prostate Biopsy	X 						X 
Prostate Specific Antigen (PSA)	X 		X		X		X 
PAE Procedure		X					
Sexual Health Inventory for Men (SHIM)	X 				X		
International Prostate Symptom Score (IPSS)	X 			X	X	X	X 

	Baseline	PAE Procedure	Visit 1	Visit 2	Visit 3	Visit 4	Unscheduled Visits
			4 Weeks (±1 week/± 7 days)	3 Months (±2 weeks/± 14 days)	12 Months (±8 weeks/±56 days)	24 Months (±8 weeks/±56 days)	
BPH related medications (5α-Reductase inhibitors, α-blockers, etc.)	X		X	X	X	X	X 
Device or Procedure-Related Adverse Events		X	X	X	X	X	X 
Urinary Evaluations (Indwelling urinary catheter use, Qmax and PVR)	X 			X	X	X	X 
Additional prostate procedures and/or imaging			X	X	X	X	X 

 Prostate biopsy within 12 months of PAE procedure

 Baseline SHIM to occur within 4 weeks of PAE procedure

 Baseline IPSS to occur within 4 weeks of PAE procedure

 Within timeframe consistent with standard of care

 Unscheduled visits may include one or more of the identified evaluations

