## **8 Statistical Considerations**

### **8.1 Endpoint Definitions**

#### **8.1.1 Primary Endpoints**

The primary endpoint is the IPSS at 12 months.

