### **8.5.1.5 Missing Data**

All attempts will be made to limit the amount of missing data. For all analyses of the primary endpoints, the number of observations available will be reported so the reader can assess the impact of missing data. For all clinical endpoints except for the patient-reported outcome measurements, an adjustment to the denominator will be made based on the amount of evaluable data. For each visit (or reporting time point), the event rate will be calculated as the number of subjects with certain event terms over the number of evaluable subjects. The evaluable subjects at each reporting time point include all subjects who are enrolled and

- 1) had an event within (on or before) the reporting cutoff days, or

- 2) had a follow-up at or after the lower limit of the reporting window, or
- 3) the withdrawal consent date/recorded lost-to-follow-up date at or after the lower limit of the reporting window.

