### 8.5.2.1 Missing Data

Missing data for the IPSS will be imputed as the age-specific average for that time point. Also, a tipping point analysis will be performed where the analysis will be performed, excluding the missing data. The number of missing data points it takes to tip the results from one direction to the other will be reported.

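### No rule lets an IPSS recorded as unscheduled but dated inside the 12-month window serve as the 12-month value; read literally, an age average replaces it

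*Combined protocol and SAP*

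**What the plan says.** - **Endpoint.** Section 8.1.1: "The primary endpoint is the IPSS at 12 months". Table 1 sets the visit at "12 Months (±8 weeks/±56 days").
- **Assignment to time points.** Under the visit-windows item of section 8.5.1.2, "visit assessments will be analyzed for each analysis time point according to the study visit entered in the electronic Case Report Form (eCRF"), and the sentence ends "to determine if the visit was within compliance". The section defines Study Day but does not use it to place an assessment at a time point. The sentence allows for exceptions, but none is given for the IPSS.
- **Unscheduled scores.** Table 1 has a separate column for unscheduled visits and marks the IPSS in it. Its footnote 5 reads "Unscheduled visits may include one or more of the identified evaluations". Section 6.6 adds: "Data will also be collected for additional evaluations that occur at any times outside of the above protocol-defined timepoints". The list of unscheduled measurements in section 8.1.3 does not include the IPSS, so no analysis is named for these scores.
- **Missing scores.** Section 8.5.2.1: "Missing data for the IPSS will be imputed as the age-specific average for that time point". The same section plans a further analysis that leaves missing values out. The mixed model in section 8.5.3.1 does not impute.

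**The concern.** The plan can hold a measured score from the right period and still treat the man as missing. Whether his own answer or an average of other men enters the primary endpoint depends on how the site labelled the form.

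This need not be neutral. Men seen outside the schedule may well be those who came back with persistent or recurrent symptoms. The protocol also contains a route to the problem. Section 7 ends data collection for a man who has another BPH procedure. Suppose he returns with symptoms on day 320, completes an unscheduled IPSS, and has such a procedure on day 335. He will then have no later Visit 3, and the unscheduled score is his only value from the 12-month window. Replacing it with the average of men who did attend would make the 12-month result look better than the data collected.

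The label rule also has a converse. A form labelled Visit 3 but completed well after day 421 would count as the 12-month value, and the plan does not say whether such values are flagged in the analysis.

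**Working it through.** The plan gives no figure for this point, so there is none to reproduce. The stated precision target, ±1 unit (section 8.2), serves as the yardstick.

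**1. Window.** Taking 12 months as 365 days: 365 − 56 = 309 and 365 + 56 = 421.

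**2. Path of one score through the plan.** Take a man with an IPSS on day 350, filed as unscheduled, and no Visit 3 form.
- Section 8.5.1.2: his label is not Visit 3, so he has no 12-month IPSS.
- Section 8.5.2.1, imputed analysis: he receives the age-specific average.
- Section 8.5.2.1, analysis without missing values: he is dropped, and his score with him.
- Section 8.5.3.1, mixed model: he is not imputed, but nothing says that unscheduled scores enter the model.

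**3. Size for one man (illustrative scores).** Baseline 22, unscheduled IPSS 19. Observed change: 19 − 22 = −3. For the age average, take 6.2, the 9-16 month mean of the earlier cohort in section 1. Imputed change: 6.2 − 22 = −15.8.

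**4. Size for the study.** Let f be the share of analysed men in this position, u their mean unscheduled score and a the age average. Imputation replaces u by a and leaves each man's baseline alone, so the mean improvement is overstated by f × (u − a). With a = 6.2, u − a is 8.8 for u = 15 and 11.8 for u = 18.

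| Assumed f | u = 15 | u = 18 |
|---|---|---|
| 1% | 0.01 × 8.8 = 0.09 | 0.01 × 11.8 = 0.12 |
| 3% | 0.03 × 8.8 = 0.26 | 0.03 × 11.8 = 0.35 |
| 5% | 0.05 × 8.8 = 0.44 | 0.05 × 11.8 = 0.59 |

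Dropping these men instead gives the same shift if their baselines resemble the others', so the two planned analyses would agree without either being a check on this.

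**5. Cross-check from the plan's missing-data allowance.** Section 8.3 allows 10% missing, or 50 of 500. If a share s of those men have an in-window unscheduled score that differs from the average by d points, the shift is 0.10 × s × d. For d from 2 to 10:
- s = 10% (5 men): 0.02 to 0.10
- s = 50% (25 men): 0.10 to 0.50
- s = 100% (50 men): 0.20 to 1.00

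The last line is an outer bound, because the 10% also covers missing baselines.

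**6. Comparison with precision.** At SD 8.5 and 450 men, the simple 95% half-width, without a finite-population factor, is 1.96 × 8.5 / √450 = 0.79. Recovering 25 scores gives 1.96 × 8.5 / √475 = 0.76. The gain in precision is trivial; the possible bias is what matters.

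**The case against.** The strongest reply is that the plan is silent rather than wrong. A reader might infer that the plan orders unscheduled scores to be discarded. It does not: no section says so, and the assignment sentence is muddled, since it ends by speaking of visit compliance. Section 6.6 describes additional evaluations as those outside the defined timepoints, so a site could properly enter a day-350 IPSS as Visit 3. The questionnaire can be returned by mail or email (section 6.5), and section 7 asks sites to reschedule a missed visit within its window. The problem therefore needs three things together: an in-window score, an unscheduled label, and no Visit 3 IPSS in 16 weeks. All this stands, and it is why the share is probably small. It does not supply the missing rule.

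Two wider readings fail.
- A reader might infer that the plan uses two definitions of 12 months, because section 8.5.1.5 counts a subject as evaluable if he "had a follow-up at or after the lower limit of the reporting window". That section excludes patient-reported outcomes, and it sets denominators for event rates; it does not choose a questionnaire score.
- A reader might extend the point to the SHIM. Table 1 schedules no SHIM at unscheduled visits, so there is no planned score to recover.

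Finally, a fallback to unscheduled scores brings in values from symptom-driven visits, while other men without Visit 3 are still imputed. This stands as a modest cost. It is a reason to report how many such values are used, not to prefer an average of other men to a man's own in-window answer.

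**Conclusion.** The point holds as a gap with a literal consequence. Time points follow the visit label, nothing maps an in-window unscheduled IPSS to 12 months, and a man with only that score is imputed or dropped. If such men are more symptomatic, the overstatement is about 0.1 point at a 1% share and 0.4 to 0.6 at 5%, below the simple half-width of 0.79 in each case. The shares, the unscheduled means of 15 to 18 and the use of 6.2 as the age average are all assumptions. The documents give neither the number of such men nor their scores, so they do not support a claim that the primary result is materially biased. The change is worth making because it is nearly free and settles before analysis a choice that affects the primary endpoint.

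**What to change.** In section 8.5.1.2, for the IPSS only, state this order for the 12-month value:

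1. Use the Visit 3 IPSS when there is one.
2. If there is none, use the unscheduled IPSS nearest the target day within the protocol window (days 309 to 421).
3. Apply the imputation in section 8.5.2.1 only when neither exists.

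Keep Visit 3 values dated outside the window in the primary analysis, report their number, and add a sensitivity analysis that excludes them. Report how many 12-month values come from unscheduled visits, since these may be symptom-driven.

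The cost is a few lines of SAP text and a small programming change. No new data are needed: assessment dates already feed Study Day, and Table 1 already provides for the unscheduled IPSS.
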